# 13.6 Withdrawal of Participants

There is no risk associated with withdrawal from the study. Participants may be withdrawn from the study if either the PI or MI feels that their continued participation would jeopardize the participant's health. In case of withdrawal, early termination procedures would be followed including documentation of adverse events, drug side effects, and reason for withdrawal. Any remaining study drug would also be collected at this time.

# 13.7 Stopping Rules

This study does not involve major risk for participating. Nevertheless, in addition to monitoring recruitment, we also will monitor the rates of adverse events in our participants. The study investigators will alert the IRB, if a larger than reasonably expected adverse event rate occurs in our participants.

# 13.8 Data Collection, Storage, and Confidentiality

#### **13.8.1 Protection of Stored Data**

Protection of subject privacy will be accomplished by a variety of stringent security measures. All medical records will be stored in locked areas, and access to these areas is limited to the clinic support staff, the Director of the clinical facilities, PIs at PBRC, and authorized designees of the PI. Volunteer medical records will be filed according to an assigned volunteer ID number. All forms on the chart, with the exception of the consent form, will display only the ID number, with no subject-identifiable information. All of these will be kept separate from records with names and other personal information. The only people who will know that these patients are research participants are members of the research team (including research collaborators). However, participant information will be shared with ApneaMed via prescription to obtain required PAP devices. No information about them, or provided by them during the research, will be disclosed to others without their written permission, except if it is necessary to protect their rights or welfare (for example, in case of injury or emergency care), or if it is required by law. When the results of the research are published or discussed in conferences, no information will be included that would reveal the identity of the individuals. Participants will be identified by codes when the data gathered in this procedure is presented or published. Authorized representatives of the NIH may need to review records of individual participants. As a result, they may see their name; but they are bound by rules of confidentiality not to reveal the participants' identity to others. Electronic data storage is secured with password protection and similarly restricted with only the PI and authorized persons having access to databases containing confidential clinical records (i.e. those containing name, social security number, or other identifying information). Electronic communication will involve only unidentifiable information.

### 13.8.2 Confidentiality

PBRC complies with the federal 1996 Health Insurance Portability and Accountability Act (HIPAA). Specifically, PBRC protects the privacy and confidentiality of medical records and information contained in medical records of persons who are participants of research projects, including all protected health information (PHI) as defined by the HIPAA privacy Regulations. PHI of research participants and the use or disclosure of such information is governed by PBRC research policies as well as Common Rule, FDA regulations, and other applicable laws.

PBRC and study PI (the person chiefly responsible for the record) protect the privacy of research participants and their PHI collected during a research project. PBRC will not use or disclose existing PHI or PHI created during a research project, unless the:

• Subject signs both (a) a HIPAA Authorization for use and disclosure of PHI using an approved Authorization Form or other form containing all the elements of legally effective HIPAA authorization; and (b) the informed consent to participate in research form approved by IRB; or

- IRB grants a waiver to the requirement of obtaining a signed HIPAA authorization Form, or
- IRB approved protocol uses properly de-identified PHI

All volunteers are assured of their anonymity and confidentiality both verbally and in the informed consent.

#### 13.8.3 ClinicalTrials.gov Requirements

The clinical study is registered on *ClinicalTrials.gov*, in accordance with NIH recommendations. The unique NCT identifier (NCT04530747) will be included in all future Progress Reports and publications.

#### 14 DATA MANAGEMENT AND ANALYSIS

All questionnaire data will be stored using REDCap. Other participant data will be stored on secured servers at Pennington Biomedical.

#### 14.3 Data management

The data management will be conducted by the Pennington Biomedical Research Computing Group. There will be limited access to all data including locked cabinets for paper files and password protected computers for electronic data.

**REDCap**, a web-based application used to build and manage surveys and databases, will be used for questionnaire collection in this study. REDCap (Research Electronic Data Capture) is a secure, web-based application that is flexible enough to be used for a variety of types of research. REDCap provides an intuitive user interface that streamlines project development and improves data entry through real-time validation rules (with automated data type and range checks). REDCap also provides easy data manipulation (with audit trails for reporting, monitoring and querying patient records) and an automated export mechanism to common statistical packages (JMP, SPSS, SAS, Stata, R/S-Plus).

#### 14.4 Statistical Plan:

Statistical analyses will be performed by [name] with support from the LA CaTS Center (U54-GM104940) in accordance with a pre-specified statistical analysis plan.

#### 14.4.1 Sample Size Considerations

Although a formal power analysis was not feasible in this randomized, crossover pilot trial, we can expect significant improvements to be detectable with up to 18 completers for whole-body insulin sensitivity determined by Matsuda Index. Importantly, the proposed trial will be used to generate first-of-its-kind preliminary data for our investigative team to establish effect sizes and, therefore, develop power calculations as part of a future R01-level grant application.

### 14.4.2 Statistical Analyses

The primary outcome is insulin sensitivity via Matsuda Index. We will use mixed effect linear models, accounting for correlation over time and treatment to assess outcome difference in metformin and placebo treated groups. Primary analysis will be conducted on all study participants who have taken one dose of the study drug and used CPAP for at least one night. Sensitivity analyses will be conducted on per-protocol sample of subjects adherent to the study interventions. Publications will acknowledge the limitation of small sample and any other weaknesses.

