#### 2. STUDY AIMS

Our overarching hypothesis is that in addition to improving insulin sensitivity (IS) via modulating hepatic gluconeogenesis metformin therapy will counteract the elevated cellular senescence in OSA patients using PAP, and thereby reduce tissue IR and dysfunction. Specifically, we propose that cellular senescence continues to persist and propagate in tissue of OSA patients undergoing PAP treatment. Therefore, anti-senescent therapeutics such as metformin would benefit OSA patients by improving tissue function and consequent metabolic profile. Notably, the role of increased cellular senescence in obesity- and age-related metabolic disorders is being increasingly recognized. 

To test our hypothesis, we will conduct a double-blind, placebo-controlled, randomized clinical trial in nondiabetic OSA patients (Apnea hypopnea index, AHI≥15 events/h, HbA1c<6.4%) (fig 1). All participants will be provided PAP therapy and adherence will be monitored via monthly compliance visits. In addition, participants will be randomized to receive either metformin (2g/day, n=10) or matching placebo (n=10) for 3 months. Study measures will be collected at 0 and 3 months to address the following specific aims:

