#### AIM 1: To determine the effects of metformin + PAP on whole body insulin sensitivity (IS).

Hypothesis: Addition of metformin to PAP therapy in OSA patients will enhance reduction in IR. Measures derived from oral glucose tolerance test including Matsuda index (whole body-IS) and ISI-FAA (AT-IS) will be used to longitudinally examine changes in IS to inform about metabolic risk reduction in OSA patients.

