# 9. METHOD FOR ASSIGNING PARTICIPANTS TO TREATMENT GROUPS (RANDOMIZATION)

After confirmation of eligibility criteria, participants will be randomized to receive either placebo or metformin in a 1:1 ratio. [name], the study statistician, will perform the randomization, and the study drug assignment will be implemented by [name], investigational pharmacist. Randomization will be done using a dynamic allocation based on age and OSA severity determined by Apnea Hypopnea Index (AHI).

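### The primary Matsuda analysis states neither its between-group contrast nor its use of baseline Matsuda; specify the Month-3 difference by baseline-adjusted ANCOVA

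*Combined protocol and SAP*

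**What the plan says.** Section 14.4.2 names the endpoint, "The primary outcome is insulin sensitivity via Matsuda Index", and then gives the only description of the primary model in the supplied text: "We will use mixed effect linear models, accounting for correlation over time and treatment to assess outcome difference in metformin and placebo treated groups". It lists no fixed effects, timepoint or contrast, and gives no role to the baseline value.

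Other sections bear on the reading without settling it:
- Section 2: "Study measures will be collected at 0 and 3 months to address the following specific aims". There is one baseline and one follow-up value per participant.
- Aim 1: the indices "will be used to longitudinally examine changes in IS to inform about metabolic risk reduction in OSA patients".
- Section 9: "Randomization will be done using a dynamic allocation based on age and OSA severity determined by Apnea Hypopnea Index (AHI"). Baseline Matsuda is not a balancing factor.
- Section 14.4.1: "we can expect significant improvements to be detectable with up to 18 completers for whole-body insulin sensitivity determined by Matsuda Index". No effect size, SD, correlation, alpha or power accompanies this. The data are also meant "to establish effect sizes and, therefore, develop power calculations as part of a future R01-level grant application".
- Section 14.4: analyses will be done "in accordance with a pre-specified statistical analysis plan". No further model detail appears in the supplied text.

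**The concern.** At least two different estimates fit the same sentence. A model of both visits with group, time and group-by-time, and baseline means left free, estimates the difference in mean change. A model of both visits with a common baseline mean estimates the baseline-adjusted Month-3 difference, as ANCOVA does. Given two visits and an aim worded around change, the first is the more natural reading. That is an inference; the sections do not say it.

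Both are valid in a randomised trial, but they are not interchangeable at this size. Because the trial is meant to supply effect sizes for a later power calculation, the estimate and its interval are its main product. An unsettled choice leaves both undefined, and the likelier choice gives away precision that data already scheduled for collection could provide.

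**Working it through.** **The plan's own figure.** The statement about 18 completers cannot be reproduced, because Section 14.4.1 says a formal power analysis was not feasible and gives no inputs.

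**Inputs.** From the documents: 1:1 allocation, two measurement times, and up to 18 completers, taken as n = 9 per arm. Parallel arms are assumed, as Sections 2 and 3 describe, although Section 14.4.1 calls the trial a crossover. Assumed, because the documents give no values: a true effect of 1 SD (the baseline SD), two-sided 5%, a baseline-to-Month-3 correlation rho of 0.3/0.5/0.7/0.8, and, to begin with, equal SDs at both visits.

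**Step 1: standard errors (SD units).**
- Change score: SE = sqrt(2(1−rho) × 2/n), 2n−2 = 16 df.
- ANCOVA: SE = sqrt((1−rho²) × 2/n × 15/14), 2n−3 = 15 df. The 15/14 is the average cost of chance baseline imbalance: 1 + E(t²)/16, with E(t²) = 16/14 on 16 df.

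Example at rho 0.5: change, sqrt(1.00 × 0.2222) = 0.471, times 2.120 gives a half-width of 1.00. ANCOVA, sqrt(0.75 × 0.2222 × 1.0714) = 0.423, times 2.131 gives 0.90.

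**Step 2: results, equal SDs.** Power is from the noncentral t, averaged over chance baseline imbalance for ANCOVA. Disagreement is from 40,000 simulated trials per rho, with both analyses applied to the same data.

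| rho | Power, change | Power, ANCOVA | 95% CI half-width, change | 95% CI half-width, ANCOVA | 5% verdicts differ | Median gap in estimate |
|---|---|---|---|---|---|---|
| 0.3 | 0.39 | 0.52 | 1.18 | 0.99 | about 23% | 0.20 SD |
| 0.5 | 0.51 | 0.60 | 1.00 | 0.90 | about 19% | 0.14 SD |
| 0.7 | 0.73 | 0.77 | 0.77 | 0.74 | about 12% | 0.08 SD |
| 0.8 | 0.88 | 0.89 | 0.63 | 0.62 | about 6% | 0.05 SD |

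**Step 3: break-even, equal SDs.** The variance ratio ANCOVA/change is (1+rho)/2 × 15/14. It equals 1 at rho = 28/15 − 1 = 0.867. For interval width, which also reflects the lost degree of freedom, break-even is about 0.85. At rho 0.9 the half-widths are 0.453 (ANCOVA) and 0.447 (change).

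**Step 4: unequal SDs.** Let k be the Month-3 SD divided by the baseline SD. In units of baseline variance and leaving out the common factor 2/n, the change score has variance 1 + k² − 2k·rho, which equals k²(1−rho²) + (k·rho − 1)². ANCOVA has k²(1−rho²) × 15/14. Adjustment therefore removes (k·rho − 1)² and pays k²(1−rho²)/14.
- At k = 1.2 and rho 0.7: change 1 + 1.44 − 1.68 = 0.760; ANCOVA 1.44 × 0.51 × 1.0714 = 0.787; ratio 1.04.
- At k = 1.2 and rho 0.8: 0.520 against 0.555; ratio 1.07.
- Break-even at k = 1.2: at rho 0.62 the gain is 0.0655 and the price 0.0633; at 0.63 they are 0.0595 and 0.0620. Adjustment starts to lose at about 0.63.
- Because the removed term is a square and cannot be negative, the ratio never exceeds 15/14, a loss of at most about 7% of variance.
- With k below 1 the comparison favours adjustment more.

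**Step 5: which model gives which estimate.** In four simulated data sets, the free-baseline group-by-time term equalled the change-score difference, and the common-baseline two-visit estimate equalled ANCOVA, each to four decimals. In one data set at rho 0.3 the two estimates were 0.6683 and 0.2414.

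**The case against.** **The model may already be fixed elsewhere.** Section 14.4 cites a pre-specified plan, and Section 14.4.2 may only summarise it. This stands. A reader might infer that the choice is open until unblinding; the documents support only that it is not stated in the supplied text.

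**Change is a legitimate target, and the gain is modest at high correlation.** This also stands. The change score is unbiased, and at rho 0.7 and 0.8 adjustment adds 4 and 1 points of power. The large gains need a correlation of 0.3 to 0.5. A reader might infer that the natural reading is invalid or biased; it is neither.

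**Adjustment is not always more precise.** Correct. The 0.87 break-even requires equal SDs, and nothing in the documents supports that. Matsuda is a reciprocal square-root index (Section 11.7) and both arms start PAP, so the spread may change. What remains is an asymmetry: the possible loss is capped at 7% of variance, whereas at rho 0.3 with equal SDs the gain is about 30% (ratio 0.65 × 15/14 = 0.70).

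**A worse reading exists.** The sentence could be taken to mean a treatment main effect averaged over both visits. That would estimate half the Month-3 effect, with power 0.24/0.21/0.19/0.18 at the four correlations. The wording does not exclude it, but nothing indicates that it is intended, and an aim about change points away from it. The point does not rest on it.

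**Conclusion.** The concern holds in a limited form. The supplied text leaves the primary contrast and the role of baseline Matsuda unstated, and its most natural reading is an analysis that is valid but usually less precise than one using the baseline value as a covariate. Under the stated assumptions, the difference is 13 points of power at rho 0.3, 9 at 0.5, 4 at 0.7 and 1 at 0.8, and the choice changes the 5% verdict in roughly one trial in four to one in seventeen.

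The sizes depend on rho and on the SD ratio, neither of which is in the documents. The need to name one contrast depends on neither. The material does not show that the planned analysis is biased, that the plan commits to a change score, that no pre-specified model exists, or that adjustment wins at every correlation. This is a change that should be made; it is not a fatal flaw.

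**What to change.** Keep the existing sentence, because it is the only method given for the other outcomes in Aims 1 to 3, and add after it:

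*For the primary outcome, the analysis estimates the metformin minus placebo difference in Matsuda index at Month 3 by ANCOVA adjusted for baseline Matsuda, with 95% CI. A common-baseline two-visit mixed model with a small-sample (Kenward-Roger) correction to the standard error and degrees of freedom is a sensitivity analysis.*

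One model should be named as primary. The two share a point estimate but not necessarily a standard error. In 300 simulated trials per rho at 0.3, 0.5 and 0.7, the uncorrected common-baseline standard error was a median 0.95 of the ANCOVA one, and 5% verdicts differed in 5 to 7% of trials. The sensitivity model also keeps participants who have only a baseline value.

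Adjustment for the allocation factors, age and AHI, can stay an optional sensitivity analysis with the covariate form fixed before unblinding. In simulations with 18 completers, adding them cost about 3 to 7 points of power when they were not prognostic.

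If the separate plan cited in Section 14.4 already specifies the model, check that it adjusts for baseline and align Section 14.4.2 with it.

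Cost: wording only, since the baseline OGTT is already scheduled; one degree of freedom; and a small possible loss of precision if the correlation is high or the Month-3 spread exceeds that at baseline.

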### 3. RESEARCH DESIGN

We will conduct a double-blind, placebo-controlled, randomized proof-of-concept RCT in 20 non-diabetic OSA participants (fig 1). After baseline measures are obtained, all participants will be asked to initiate and adhere to PAP therapy. Participants will be randomly assigned in a 1:1 ratio to receive placebo or metformin for 3 months.

All study visits will take place at Pennington Biomedical Research Center (PBRC). Qualifying sleep study will be conducted at PBRC and the data will be shared with our research collaborators (LSUHSC-NO, [name]) and ApneaMed to determine eligibility and obtain PAP devices. PAP devices will be provided at PBRC

**Fig 1:** Schematic of the study design. Study measures will be obtained at baseline and at 3-month follow-up. Monthly compliance visits will monitor adherence to PAP and study drug. Participants will also undergo comprehensive phenotyping to assess metabolic risk.

and treatment will be administered online. Eligible participants will remain in the study for up to 4 months. The study will take place over a period of 1 year.

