#### 5. STUDY POPULATION

#### 5.1 Subject Population

We will enroll up to 20 untreated OSA patients. The study may need to screen up to 60 participants to enroll 20 participants in the RCT.

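### Allocation is balanced on age and AHI, but the stated primary model names neither; if either predicts Month-3 Matsuda beyond baseline, the test is conservative and power is lost

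*Combined protocol and SAP*

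**What the plan says.** Section 9 sets the allocation: "Randomization will be done using a dynamic allocation based on age and OSA severity determined by Apnea Hypopnea Index (AHI". It gives no cut-points, assignment probability or algorithm. Section 3 describes parallel arms: "Participants will be randomly assigned in a 1:1 ratio to receive placebo or metformin for 3 months".

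Section 14.4.2 states "The primary outcome is insulin sensitivity via Matsuda Index" and then gives the model in one sentence: "We will use mixed effect linear models, accounting for correlation over time and treatment to assess outcome difference in metformin and placebo treated groups". It lists no covariates. It also does not say which contrast is primary, whether treatment-by-time or the Month-3 difference. Section 14.4 refers to a pre-specified analysis plan, but no text supplied adds the allocation factors or a re-randomisation test.

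The outcome is measured twice (Section 2): "Study measures will be collected at 0 and 3 months to address the following specific aims". On size, Section 5.1 says "We will enroll up to 20 untreated OSA patients" and Section 14.4.1 says "we can expect significant improvements to be detectable with up to 18 completers for whole-body insulin sensitivity determined by Matsuda Index", with no effect size, SD, alpha or power. Section 14.4.1 also calls the design a crossover: "Although a formal power analysis was not feasible in this randomized, crossover pilot trial". That conflicts with Sections 2 and 3 and is a separate matter. Parallel arms are assumed below.

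**The concern.** Balancing on a factor removes most of that factor's contribution to the chance difference between arms. A model without the factor still counts the contribution as residual noise. If the factor is prognostic for the quantity compared, the reported standard error describes a less precise design than the one used. The test then rejects too seldom under the null, and the interval is too wide.

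This trial has little precision to spare. It also exists partly to supply effect sizes for a later grant application (Section 14.4.1), so a residual SD inflated in this way would carry into that planning. The same question arises for the between-arm comparisons in Aims 2 and 3. For those, Sections 1 and 2 link senescence to age-related conditions.

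**Working it through.** **Inputs.** From the documents: up to 20 randomised 1:1, up to 18 completers, visits at 0 and 3 months, allocation on age and AHI. Assumed, because the documents give nothing: two-sided 5% tests, minimisation on two dichotomised factors, assignment probability 1.0 or 0.8, and the prognostic strength of the factors.

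**1. The plan's own figure.** The statement about 18 completers cannot be reproduced without an effect size, SD, alpha and power. For scale, with 9 per arm and 80% power, the detectable difference is (1.960 + 0.842) × √(2/9) = 1.32 SD by the normal formula, or 1.41 SD with the noncentral t.

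**2. Mechanism.** Let R² be the share of variance in the analysed quantity (the change, or Month-3 given baseline) that the two factors explain, and n the number per arm.
- SE² reported without the factors ≈ σ² × 2/n.
- True SE² under perfect balance ≈ σ²(1 − R²) × 2/n.
- Ratio of SEs = 1/√(1 − R²), which is 1.054 at R² = 0.10 and 1.195 at R² = 0.30.

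Real allocation balances imperfectly, so these ratios are upper limits.

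**3. Change analysis, simulated.** With complete data this equals treatment-by-time in a two-visit mixed model. The simulation used 18 participants, single-visit SD 1, within-person correlation 0.6, and 6,000 null and 4,000 alternative runs. With no factor effect, the SD of change is √(2 × 0.4) = 0.894, so SE = 0.894 × √(2/9) = 0.42, as simulated. Power is for a difference of 1.2.

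| Share of variance in change | Assignment probability | Model SE without factors | True SE | Type I error without | Power without → with |
|---|---|---|---|---|---|
| 0% | 1.0 | 0.420 | 0.426 | 5.7% | 76% → 75% |
| 10% | 1.0 | 0.444 | 0.429 (3% excess) | 4.2% | 71% → 74% |
| 30% | 1.0 | 0.509 | 0.432 (18% excess) | 2.3% | 61% → 74% |
| 30% | 0.8 | 0.510 | 0.454 (12% excess) | 3.0% | 62% → 74% |

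**4. Baseline-adjusted Month-3 analysis, simulated.** Twenty participants were minimised, with each factor split at its median, and two dropped out at random. There were 4,000 runs per case and a true effect of 1.2 residual SD. Here r is each factor's correlation with the Month-3 residual after baseline, so two independent factors explain 2r².

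| r | 2r² | Type I error without | Power without → with |
|---|---|---|---|
| 0 | 0% | – | 64% → 60% |
| 0.2 | 8% | – | about even |
| 0.3 | 18% | 3.7–4.1% | 63–64% → 67–68% |
| 0.4 | 32% | 3.1–4.2% | 63–64% → 73–76% |

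The ranges cover both assignment probabilities and, at r = 0.4, a repeat set of runs. The interval half-width falls by 5% at r = 0.3. At r = 0.4 it falls from 1.03 to 0.89 SD, which is 14%. Monte Carlo error with 4,000 runs is √(0.05 × 0.95/4000) = 0.3 points for type I error and √(0.64 × 0.36/4000) = 0.8 points for power.

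**5. Factors that predict only the stable level.** Let the factors explain 30% of the between-person level of Matsuda and none of its change (assignment probability 1.0).
- Change analysis without the factors: model SE 0.421 against true 0.424, type I error 4.8%, power 76% without and 75% with the factors.
- Baseline-adjusted analysis without the factors: 0.401 against 0.391 (about 3% excess), type I error 4.4%, power about 80% either way.

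**6. Form of adjustment.** In a two-visit mixed model, a covariate with the same effect at both visits cancels from the within-person contrast. In one fitted example with complete data, the treatment-by-time SE was:
- without the factors: 0.38905
- with age and AHI as main effects: 0.38904
- with age-by-time and AHI-by-time terms: 0.341

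**The case against.** The strongest reply is that the gain may not exist. Nothing in the documents says that age or AHI predicts the change in Matsuda, or its Month-3 value once baseline is known. If the factors act equally at both visits, baseline takes up most of their effect. A simulation of that case used r = 0.2 to 0.4, assignment probability 0.8, within-person correlation 0.7 and an effect of 1.1 SD. It gave type I error of 4.3 to 4.9% without the factors, and adjustment lost 1 to 4 points of power (for example 83.6% to 80.5% in the baseline-adjusted model at r = 0.3). The larger gains in step 4 need r near 0.4, which is about a third of the variance left after baseline. Any error is also only conservative, in a pilot that disclaims a formal power analysis and promises to acknowledge its small sample.

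All of this stands, and it limits the size of the point. The mismatch remains: the trial allocates on two factors and does not say how the analysis treats them. Age may range from 35 to 65, and AHI has a floor of 15 and no ceiling (Section 5.2), so both can vary widely. Leaving the question open also allows covariates to be chosen after unblinding, and with about 18 completers that choice could change the result.

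**Conclusion.** The point holds in conditional form. The stated model is not aligned with the allocation. The cost is lost power and an over-wide interval if age or AHI is prognostic for Month-3 Matsuda given baseline, or for the change. The range runs from a power gain of about 12 points with adjustment (r = 0.4) to a loss of about 4 (r = 0). It rests on assumed prognostic strength, cut-points and assignment probability.

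A reader might infer three stronger things that the documents do not support.
- **That the standard error is too large whenever age or AHI is related to Matsuda.** Step 5 shows that a factor acting only on the stable level leaves a treatment-by-time analysis about correct.
- **That the plan excludes the two factors.** It is silent on covariates, and Section 14.4 points to an analysis plan whose detail is not in the text supplied.
- **That the primary result would be invalid.** The error described is conservative, so it does not inflate false positives.

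This is a cheap improvement.

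**What to change.** In Section 14.4.2, name the primary contrast and how the allocation factors enter. Suggested text: *The primary comparison is the between-arm difference in Month-3 Matsuda Index, adjusted for baseline Matsuda Index, age and log-transformed AHI.*

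If both visits are kept as outcomes in the mixed model, specify treatment-by-time as the contrast and include age-by-time and AHI-by-time terms. Main effects of age and AHI alone would leave its standard error unchanged. Use the same form for the between-arm models in Aims 1 to 3, and report the model without the two factors as supportive.

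The cost is one or two sentences and no new data, since both factors are known before randomisation. With 18 completers, a model with intercept, treatment and baseline has 18 − 3 = 15 residual degrees of freedom, and the two covariates reduce this to 13. If neither factor is prognostic beyond baseline, that costs about 4 points of power.
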